7.3. REPORTING OF UNANTICIPATED PROBLEMS, ADVERSE EVENTS AND PROTOCOL DEVIATIONS

There is a small risk that confidential information may be lost, or there may be a breach in the computer database storing personally identifiable information (PII).

The Lead Principal Investigator is responsible for detecting, documenting, and reporting unanticipated problems, adverse events (AEs), including serious adverse events (SAEs), and protocol deviations in accordance with NIH policy, IRB requirements, and federal regulations. Relatedness to the research of all serious adverse events will be determined by the PI.

Serious unanticipated problems and serious protocol deviations will be reported to the IRB as soon as possible and in writing not more than 7 days after the PI first learns of the event. Adverse events that are deemed not to be serious will be reported to the IRB as soon as possible and in writing not more than 14 days after the PI first learns of the event.

All adverse events, deviations, and unanticipated problems will be summarized and reported at the time of Continuing Review.

7.4. CRITERIA FOR INDIVIDUAL SUBJECT WITHDRAWAL FROM THE STUDY

A participant may be removed from the study at any time if the Management Team believes that it is not in the participant's best interest to continue, or if the participant is unable to comply with the requirements or Terms and Conditions.

Participation is entirely voluntary. If a participant changes her mind and wishes to withdraw her information from the study, she is free to do so without having to provide any explanation and without loss of benefits or privileges to which she is otherwise entitled. If a participant no longer wants to take part, she can change her profile preferences so that she stops receiving reminders. If she wants to withdraw her data from the database, she can contact the Coordinators to start that process; however, data that has already been de-identified and provided to outside researchers and/or data repositories before the request was received and processed cannot be retrieved.

SECTION 8. STATISTICAL ANALYSIS PLAN

8.1. ANALYSIS OF DATA/STUDY OUTCOMES

PregSourceSM will be a research registry for investigators to use. As such, we do not have any pre-planned statistical analysis. Power calculations would vary depending on the proposals investigators submit for approval.

8.2. SAMPLE SIZE, POWER ANALYSIS, AND AVAILABLE POPULATION

Given PregSourceSM's online, self-consenting process, there is no set limit to the number of participants who can enroll, and it is difficult to estimate accurately how many women will find the study, choose to enroll, and enter their data consistently.

For 2009 (the latest year for which data is currently available), the CDC reported an estimated 6,369,000 pregnancies, resulting in 4,131,000 live births (Curtin 2013). According to the Pew Research Center's Internet & American Life Project, in 2012, 72% of U.S. adults in the survey said that they had gone online in the past year to look up health information; and women were more likely than men to look up information about specific medical conditions for themselves or someone else (Fox 2013).

Conservatively, with falling birth rates reported (Curtin 2013), if only 1% of these pregnant women locate the study and 50% choose to join, the study could enroll more than 30,000 women per year. This could lead to an anticipated enrollment of 120,000 women over 4 years.

For recruitment purposes, if a participant drops out or withdraws her information, no specific effort will be made to replace her.

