2.3.1. Primary Outcome Measures

- Gestational age of delivery
- Birthweight of baby
- Maternal gestational weight gain
- Health of baby and mom

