4.2.4. Anticipated Accrual Rate

There is no limit on the number of participants in PregSourceSM. At this time it is difficult to estimate accurately how many women may choose to register, how many will enter – and continue to enter – data throughout their pregnancy, and what the accrual rate is likely to be. The immediate goal is to accrue 10,000 participants within 2 years of launch.

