4.4.3. End of Participation

Unless she withdraws from the study, a participant ends her participation in the study when her pregnancy ends due to termination, miscarriage, or stillbirth, or at 36-months post-partum. She may, however, choose to continue entering data through subsequent pregnancies.

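### Does calling the Section 8.2 enrolment projection conservative, at six times the rate implied by the accrual goal, require a change to the protocol?

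*Protocol*

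**What the plan says.** Section 8.2 takes the 2009 national figures, "an estimated 6,369,000 pregnancies, resulting in 4,131,000 live births", supposes that 1% of these pregnant women find the registry, and continues: "50% choose to join, the study could enroll more than 30,000 women per year". It then extends the result: "This could lead to an anticipated enrollment of 120,000 women over 4 years". The sentence carrying the calculation begins "Conservatively, with falling birth rates reported". The section also says, before the calculation, that enrolment is hard to estimate.

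Two other accrual figures appear. Section 4.2.4 states: "The immediate goal is to accrue 10,000 participants within 2 years of launch". The Protocol Details table gives an estimated total requested accrual of 100,000, with no time frame.

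Section 7.1.1.2 has the Operations Committee review recruitment each year against targets to which it attaches no accrual number. The 67% in that section concerns completion of questions. Section 8.1 says that no statistical analysis is pre-planned and adds: "Power calculations would vary depending on the proposals investigators submit for approval".

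**The concern.** A projection described as conservative should sit at or below what the sponsor is aiming for. This one runs at six times the average rate of the only figure the protocol calls a goal, and no sentence connects the two.

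The choice of base seems to point the same way. Section 8.2 mentions falling birth rates as a reason for caution, yet multiplies the larger of its two base figures. Under Section 4.4.3, "a participant ends her participation in the study when her pregnancy ends due to termination, miscarriage, or stillbirth", while Section 2.3.1 lists "Birthweight of baby" among the primary outcome measures. Some enrolled women will therefore never supply a birth outcome.

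Two consequences could be feared. A researcher requesting data might take 120,000 as a floor when planning a study of birth outcomes. And the annual recruitment review might judge the same accrual a success or a failure, depending on which figure it used.

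**Working it through.** **Inputs.** Pregnancies 6,369,000 and live births 4,131,000 per year; 1% locate the study and 50% of those join (all Section 8.2). Goal 10,000 in 2 years (Section 4.2.4). Estimated total 100,000 (Protocol Details).

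**1. Reproduce the protocol's figure.**
- Per year: 6,369,000 × 0.01 × 0.50 = 31,845, which is more than 30,000 as stated.
- Over 4 years: 30,000 × 4 = 120,000 as stated; unrounded, 31,845 × 4 = 127,380.
- The rounding removes (31,845 − 30,000) / 31,845 = 5.8%. This is the only visible allowance for falling birth rates.

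**2. Compare with the goal on the same time scale.**
- Goal rate: 10,000 / 2 = 5,000 per year.
- Ratio: 30,000 / 5,000 = 6.0; unrounded, 31,845 / 5,000 = 6.4.
- Combined locate-and-join rate needed for the goal: 5,000 / 6,369,000 = 0.079%, against 0.01 × 0.50 = 0.5% assumed.

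**3. Compare with the estimated total.**
- 120,000 / 100,000 = 1.2.
- At 30,000 per year, 100,000 is reached in 100,000 / 30,000 = 3.3 years; at the goal rate, in 100,000 / 5,000 = 20 years.

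**4. Try the smaller base.**
- 4,131,000 × 0.01 × 0.50 = 20,655 per year, or 82,620 over 4 years.
- This is still 20,655 / 5,000 = 4.1 times the goal rate, so the choice of base does not create the gap.
- The 82,620 counts women expected to reach a live birth if uptake does not depend on pregnancy outcome. The 100,000 counts enrolled subjects. The two should not be compared.

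**5. Ask which base is right for enrolment.** Section 3.1 admits women who are pregnant. Section 4.4.3 treats women whose pregnancies end in loss or termination as participants up to that point. Nausea, sleep, exercise, medication and ultrasound measures (Section 2.3.2) do not need a live birth, and neither does the mother's health in Section 2.3.1. Pregnancies are therefore the correct count of women who could enrol.

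**6. Ask what uses the figures.** Section 8.1 plans no analysis and leaves power to each data request. Section 1 releases data only once a critical mass has accumulated, when actual enrolment and birth counts will be known. Under Section 7.1.1.2 the Committee may recommend options to the institute's director; no figure triggers a decision by itself.

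**The case for a change.** The best case for an edit is that the label is wrong on the protocol's own numbers and costs almost nothing to correct. No source is given for the 1% or the 50%, the stated reason for caution yields only a 5.8% rounding, and three accrual figures stand unrelated. The review in Section 7.1.1.2 could turn on which one is meant. For illustration, 8,000 women in the first year (an assumed number) would be 8,000 / 5,000 = 160% of the goal rate but 8,000 / 30,000 = 27% of the projected rate.

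The observations stand: the adverb is unsupported, the figures are not expressly related, and Section 7.1.1.2 names no accrual number. The inference that the plan must change does not.
- Section 4.2.4 is the only place that calls a figure a goal, so a committee looking for its target has one natural candidate.
- That goal is described as immediate and runs from a launch in English only, with Spanish anticipated within 12 months (Section 4.2.2). Section 4.2.3 speaks of initial geographic areas and holds online advertising in reserve. A low start-up goal can coexist with a higher yearly potential, although the protocol does not spell this out.
- The base leaves out women abroad, who may join (Section 3). That omission errs on the cautious side.
- The fear about birth-outcome planning needs a researcher to rely on a conditional projection when real counts would be available. It also needs equal uptake across pregnancy outcomes. Women who join later have already passed the period of earlier losses, and the protocol gives no uptake by outcome.

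**Conclusion.** No change to the plan is needed. The Section 8.2 arithmetic is right, its base suits a count of enrolments, and a near-term goal and a conditional projection do not contradict each other. What remains is an unsupported adverb and a missing sentence relating 10,000 in 2 years, 100,000 in total and 120,000 over 4 years. The gap in rate is real, 6.0 times (6.4 unrounded), but no estimate, test, precision statement or automatic rule depends on it. The sponsor may tidy the wording at a future amendment; leaving it as it stands alters no result.

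This conclusion rests on two features of the protocol: power is worked out for each data request, and the recruitment review is advisory. If an accrual figure were later tied to a binding stopping rule or to a planned analysis, the protocol would need to say which figure applies.

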8.3. PROJECTED RECRUITMENT TIME

The current contract with Lockheed Martin covering PregSourceSM is for 3 years from September 30, 2014 – September 29, 2017. NICHD is committed to continuing PregSourceSM even after the current 3-year contract period either by extending the contract or using another solicitation as needed.

SECTION 9. HUMAN SUBJECTS PROTECTION

9.1. SUBJECT SELECTION

9.1.1. Statement of Equitability

The racial and ethnic characteristics of PregSourceSM participants will reflect the demographics of the individuals who are seeking information regarding pregnancy and interested in participating in clinical trials or research studies. With appropriate consent, no individuals who meet the inclusion criteria will be excluded from participation based on race or ethnicity (see exclusion criteria). Given the nature of pregnancy, men will not be included in sample collection.

Justification for inclusion of children

Not applicable. Participation in PregSourceSM is open to adults between the ages of 18 to 70 years who are pregnant.

In addition, we will be collecting developmental data on the infants born to the mothers.

9.2. JUSTIFICATION FOR INCLUSION OF VULNERABLE SUBJECTS

Pregnant women who have access to the Internet may join PregSourceSM. Because this study will only be collecting data, not providing or requiring any physical examinations or procedures, inclusion of pregnant women does not pose any specific risk above minimal risk to her or her fetus.

9.3. SAFEGUARDS FOR VULNERABLE POPULATIONS

The registry is only for a pregnant woman who can provide consent herself.

9.4.4. Required Human Subjects Training

The Lead Principal Investigator has verified that all investigators working on this study have completed the NIH Human Research Protections Program under OHSRP SOP 25.

9.6. ALTERNATIVES TO PARTICIPATION

Joining PregSourceSM is the participant's choice. Because participants will not receive or forego any treatment by participating in this study, the alternative is not to participate.

9.7. CONFIDENTIALITY

9.7.1. Confidentiality of Research Data

Upon completion of the Consent Form, the database will generate a study identification number for each participant. All study data will be stored using this ID number and personal contact information will be stored in a separate table.

Only the Management Team will have access to the data, and only the Coordinators will have access to the participants' identification data. Access will be limited by user role via password-protected accounts. All personnel with access to identifiable data must sign the IT Rules of Behavior from PatientCrossroads acknowledging appropriate use of the information.

As part of the Consent Form, each participant will be informed that her name and contact information will not be made public, and that her data will be de-identified and shared with approved research investigators.

In addition to having access to the data she has entered in PregSourceSM, via her password-protected account, each participant will be able to view summaries of data on the Website. She will not have access to the identifiable or individual information of any other participant, nor will she have the ability to contact other participants.

External investigators will be given access only to summarized and/or de-identified data.

Investigators for other clinical trials and studies seeking to recruit PregSourceSM participants for those studies will not be given participant contact information. Instead, the potentially eligible and interested participant will be given the investigator's contact information. It will be her choice whether to contact the investigator about the other study or not.

9.7.2. Certificate of Confidentiality

PregSourceSM will obtain a Certificate of Confidentiality to help insure participants' privacy.

9.7.3. Privacy Policy and Terms and Conditions of Use

The PregSourceSM Privacy Policy and Terms and Conditions for using the Website will be posted on the Website. All participants will be asked to view these documents and agree to them as part of the account set-up process.

9.8. CONFLICT OF INTEREST

NIH guidelines on conflict of interest have been distributed to all investigators.

There are no conflicts of interest to report for this study.

